6.1 Adjustments for Covariates

The change from baseline in the mean NRS score at Week 8 of the treatment period, the primary variable, will be analyzed using the baseline mean NRS score and dynamic allocation factors, including the presence of prior treatment with nalfurafine hydrochloride, and the presence of specific signs or symptoms to be confirmed in the screening period as covariates. The details are shown in "10.1.1.1 Analysis of the primary variable." If an imbalance is observed in the subject demographic in the FAS, the primary analysis set for efficacy, a supplementary analysis will be performed with additional items showing the imbalance as the covariates in the primary analysis.

For the changes from baseline in the itch score based on the Shiratori's severity criteria, changes from baseline in Skindex-16, and changes from baseline in 5-D Itch Scale, an analysis will be performed using baseline as a covariate for each item. Details are shown in "10.2.1.1 Changes from the baseline in the itch score based on the Shiratori's severity criteria," "10.2.2.1 Changes from baseline in Skindex-16," and "10.2.3.1 Changes from baseline in 5-D itch scale," respectively.

Statistical Analysis Plan	Protocol No. MR13A9-4
	Version: 1.0

6.2 Handling of Dropouts or Missing Data

When there is a lack in the data used for analysis, all items other than the following items will be handled as missing values, and no imputation by statistical methods will be performed. Sensitivity analyses of the primary variable will use multiple imputation. The details are shown in "10.1.1.1.2 Sensitivity analysis."

If the number of days of observation during the evaluation period is less than 4 days as of the time of calculation of the mean NRS score and the mean itch score based on the Shiratori's severity criteria at each time point, the score at that time point will be handled as missing.

If the overall score or the subscores (symptoms score, emotions score, and functioning score) of the Skindex-16 or the responses to the questions used for calculation of the total score of 5-D Itch Scale are missing, the score will be handled as missing.

Any plasma drug concentration below the lower limit of quantification (BLQ) will be treated as 0.

Any BLQ values observed in laboratory test values will be handled as the values of the quantification limit.

In the calculation of geometric mean and geometric CV, values of 0 before log-transformation will be handled as missing values.

6.3 Interim Analyses and Data Monitoring

Not performed.

6.4 Multicenter Study

Since the number of subjects per site is not large, analysis by site will not be performed.

6.5 Multiplicity

6.5.1 Multiplicity at multiple evaluation time points

Since Week 8 of the treatment period is defined as the primary evaluation time point and evaluations at other time points are handled as references, multiplicity at multiple evaluation time points is not adjusted.

6.5.2 Multiplicity among multiple items

Since the change from baseline in the mean NRS score at Week 8 of the treatment period is handled as the primary variable, and other items are handled as references, multiplicity among multiple items will not be adjusted.

6.5.3 Multiplicity among multiple groups

For the primary variable, multiplicity among multiple groups will not be adjusted because the dose-response relationship between the placebo group and the MR13A9 0.25, 0.5, and $1.0 \mu g/kg$ groups will be examined using contrasts.

Since other items are handled as references, multiplicity among multiple groups will not be adjusted.

Statistical Analysis Plan	Protocol No. MR13A9-4
	Version: 1.0

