13.5.2.1 Analysis of the primary variable

13.5.2.1.1 Primary analysis

The primary analysis will be performed using a mixed-effects model for repeated measures (MMRM) with change from baseline in the mean NRS score at each time point as an objective variable; treatment group, time point, and treatment group-by-time point interaction as fixed effects; baseline mean NRS score and dynamic allocation factors, presence of prior treatment with nalfurafine hydrochloride, and presence of specific signs or symptoms to be confirmed in the screening period, as covariates; and subject as a random effect.

The analysis will include all available data obtained at each time point between Week 1 and Week 8 of the treatment period. Estimation will be performed using a restricted maximum likelihood method. An unstructured covariance structure will be used to estimate error variance. If the unstructured covariance structure fails to provide convergence, the structure that minimizes Akaike's Information Criterion (AIC), among the Toeplitz, first-order autoregressive, and compound symmetry structures, will be used. The degree of freedom will be adjusted with the Kenward-Roger method.

For the primary variable and the change from baseline in the mean NRS score at Week 2 of the treatment period, contrasts will be used to determine the dose-response relationship for the placebo group and the MR13A9 0.25, 0.5 and 1.0 μ g/kg groups. Contrast patterns (placebo, 0.25, 0.5, 1.0 μ g/kg) to be used will include (3, 1, -1, -3), (2, 2, -1, -3), (1, 1, 1, -1, -1), (3, -1, -1, -1), and (3, 1, -2, -2).

The adjusted mean change at each time point for each group and its two-sided 95% confidence interval will be presented. The adjusted mean between-difference in the change at each time point for the placebo group and the MR13A9 0.25, 0.5, and 1.0 μ g/kg groups and its two-sided 95% confidence interval as well as the p value will be presented.

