All statistical tests will be performed using a two-sided significance level of 5%; however, a two-sided significance level of 15% will be used for the analysis of between-group imbalance. Summary statistics will be presented as the number of subjects, mean, standard deviation, minimum, median, maximum, and quartile. Unless otherwise specified, data will be tabulated by group and by time point. Week 0 will be the baseline.

SAS System Release 9.4 for Windows (SAS Institute Inc.) will be used to conduct the analysis.

4. Analysis Sets

The analysis sets are defined as follows. When the full analysis set (FAS) and the per protocol set (PPS) are used as analysis sets, analyses will be performed based on the treatment group to which each subject has been allocated. When the safety set (SS) and the pharmacokinetic analysis set (PKS) are used as analysis sets, analyses will be performed based on the treatment group in which each subject has been actually treated.

- FAS: Population of subjects, excluding the following subjects: subjects with GCP violations, untreated subjects, discontinued subjects before entry to the treatment period, some of the ineligible subjects, and subjects with no available mean NRS score at baseline (Week 0)
- PPS: Population of subjects, excluding the following subjects from the FAS: ineligible subjects, discontinued subjects, deviators, and subjects with broken emergency key codes, as the subjects to be excluded from the PPS

Statistical Analysis Plan	Protocol No. MR13A9-4
	Version: 1.0

- SS: Population of subjects, excluding the following subjects: subjects with GCP violations, untreated subjects, and discontinued subjects before entry to the treatment period
- PKS: Population of subjects, excluding the following subjects from the SS: subjects with no available plasma drug concentration data

Correspondence of the analysis items and the analysis sets is shown in Table 4-1.

Table 4-1 Analysis Items and Analysis Sets

Endpoints	Analysis items	Analysis sets
Demographic and other baseline	Subject demographics	FAS, PPS, SS, PKS
characteristics	Other	SS
Treatment compliance	All items	FAS, SS
Efficacy	Primary variable (primary analysis)	FAS (primary analysis set), PPS
	Other	FAS
Pharmacokinetics	All items	PKS
Safety	All items	SS

5. Analysis Groups

- MR13A9 0.25 μg/kg group: Subjects allocated to or treated with MR13A9 0.25 μg/kg
- MR13A9 0.5 μg/kg group: Subjects allocated to or treated with MR13A9 0.5 μg/kg

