10.1.1.1 Analysis of the primary variable

10.1.1.1.1 Primary analysis

The primary analysis will be performed using a mixed-effects model for repeated measures (MMRM) with the change from baseline in the mean NRS score at each time point as an objective variable; treatment group, time point, and treatment group-by-time point interaction as fixed effects; baseline mean NRS score and dynamic allocation factors, including the presence of prior treatment with nalfurafine hydrochloride, and the presence of specific signs or symptoms to be confirmed in the screening period, as covariates; and subject as a random effect.

The analysis will include all available data obtained at each time point between Week 1 and Week 8 of the treatment period. Estimation will be performed using a restricted maximum likelihood method. An unstructured covariance structure will be used to estimate error variance. If the unstructured covariance structure fails to provide convergence, the structure that minimizes Akaike's Information Criterion (AIC), among the Toeplitz, first-order autoregressive, and compound symmetry structures will be used. The degree of freedom will be adjusted with the Kenward-Roger method.

For the primary variable and the change from baseline in the mean NRS score at Week 2 of the treatment period, contrasts will be used to determine the dose-response relationship for the placebo group and the MR13A9 0.25, 0.5, and 1.0 μ g/kg groups. Contrast patterns (placebo, 0.25, 0.5, 1.0 μ g/kg) to be used will include (3, 1, -1, -3), (2, 2, -1, -3), (1, 1, 1, -1, -1), (3, -1, -1, -1), and (3, 1, -2, -2).

The number of subjects, adjusted mean of the change, standard error, and two-sided 95% confidence interval in each group at each time point will be presented, and the adjusted mean and standard error will be presented in graphs. The adjusted mean between-group difference in the change at each time point for the placebo group and the MR13A9 0.25, 0.5, and $1.0~\mu g/kg$ groups and its two-sided 95% confidence interval as well as the p-value will be

Protocol No. MR13A9-4
Version: 1.0

presented. P-values will be presented for each contrast pattern used to examine the dose-response relationship.

Assessment time points: Weeks 1, 2, 3, 4, 5, 6, 7, and 8

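### SAP 6.5.3 waives adjustment because contrasts are used, but five contrasts are tested at Week 8 with no rule for which result shows a dose-response

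*SAP*

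**What the plan says.** - SAP 6.5.3, on comparisons among groups: "For the primary variable, multiplicity among multiple groups will not be adjusted because the dose-response relationship" will be examined using contrasts.
- SAP 3 (General Matters): "All statistical tests will be performed using a two-sided significance level of 5" per cent. The only exception is the check of between-group imbalance.
- SAP 10.1.1.1.1 and Protocol 13.5.2.1.1 apply the same five patterns to the primary variable (Week 8) and to Week 2. In the protocol's words, "contrasts will be used to determine the dose-response relationship for the placebo group" and the three dose groups. The SAP adds: "P-values will be presented for each contrast pattern".
- From the second pattern on, the SAP list reads "2, 2, -1, -3), (1, 1, 1, -1, -1), (3, -1, -1, -1), and (3, 1, -2, -2". The third pattern therefore has five coefficients for four groups, and the protocol prints the same string.
- SAP 10.1.1.1.1 also reports each dose against placebo with a confidence interval and p-value: "The adjusted mean between-group difference in the change at each time point for the placebo group" and the dose groups.
- SAP 6.5.1 says "evaluations at other time points are handled as references", and SAP 6.5.2 says "other items are handled as references".
- Protocol 7.6.2 gives 91.7% power at Week 8 for (3, 1, -2, -2). It then adds that power exceeds 80% for 0.5 or 1.0 μg/kg against placebo. It does not make that contrast the deciding test.

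**The concern.** Using contrasts removes the need for adjustment only if one contrast, fixed in advance, carries the conclusion. With five, each tested at 5%, the chance of at least one false positive exceeds 5% unless a rule says how the five combine. The plan has no such rule.

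The waivers elsewhere in SAP 6.5 do not fill the gap. They cover other time points and other items, whereas the five contrasts concern the primary variable at the primary time point. The three Week 8 comparisons with placebo do too, so their status is also unstated.

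Determining the dose-response is the study's stated objective (Protocol 3). Without a rule, what counts as having shown it can be settled after the p-values are known.

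**Working it through.** **Inputs.** Protocol 7.6.2: 60 per group; Week 8 differences from placebo of -0.6, -1.3 and -1.3; SD 2.5; two-sided 5%. Protocol 7.5.1: allocation 1:1:1:1. Contrast patterns: SAP 10.1.1.1.1. Assumed: equal groups and complete Week 8 data, giving 240 - 4 = 236 df and a single-test critical value of 1.970. The third pattern is read as (1, 1, -1, -1), with alternatives shown.

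**1. Reproduce the stated power.** Noncentrality = |Σcμ| / (SD × √(Σc²/n)).
- Week 8, (3, 1, -2, -2): Σcμ = -0.6 + 2.6 + 2.6 = 4.6 and Σc² = 18. The standard error is 2.5 × √(18/60) = 1.369, so the noncentrality is 3.36. Noncentral t gives 91.7%, as stated.
- Week 2 (-0.4, -0.8, -0.8; SD 1.9): 2.8 / 1.041 = 2.69, giving 76.4%, as stated.
- 0.5 or 1.0 against placebo: 1.3 / (2.5 × √(2/60)) = 2.85, giving about 81%, consistent with the protocol.

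So the plan's power is that of one contrast tested alone at 5%.

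**2. Correlation of the contrasts.** With equal groups, the correlation is Σab / √(Σa² Σb²). For (3, 1, -1, -3) and (3, 1, -2, -2) it is 18 / √(20 × 18) = 0.95. For (2, 2, -1, -3) and (3, -1, -1, -1) it is 8 / √(18 × 12) = 0.54. All ten pairs lie between 0.54 and 0.95. The independence figure, 1 - 0.95⁵ = 22.6%, therefore does not apply.

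**3. Two-sided error with no drug effect** (4 million simulated sets of four group means, t with 236 df):

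| Rule | Error |
|---|---|
| One named contrast decides | 5.0% |
| All five must be significant | 0.9% |
| Any one of five suffices | 10.8% (5.4% in the benefit direction, nominal 2.5%) |
| Any one, four well-formed patterns only | 10.1% |
| Any one, third pattern read as (1, 1, 1, -3) | 12.5% |

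**4. Maximum-contrast test.** The critical |t| that holds 5% is about 2.31 (nominal p about 0.022) with (1, 1, -1, -1), and about 2.38 (nominal p about 0.018) with (1, 1, 1, -3).

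**5. Power at the planned means:**

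| Test | Third pattern (1, 1, -1, -1) | Third pattern (1, 1, 1, -3) |
|---|---|---|
| (3, 1, -2, -2) alone at 5% | 91.7% | 91.7% |
| Any of five, unadjusted | 94.6% | 94.4% |
| Max-\|t\|, at least one contrast | 89.4% | 87.7% |
| (3, 1, -2, -2) at the max-\|t\| critical value | 85.1% | 83.6% |

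**6. Other response shapes** (SD 2.5, third pattern read as (1, 1, -1, -1)).
- Assumed differences of 0, -0.6 and -1.3, with no plateau: (3, 1, -2, -2) alone has 79% power and max-|t| has 86%.
- The non-Japanese differences in Protocol 7.6.2 (-1.8 at 0.5, -0.8 at 1.0), with -0.6 assumed at 0.25: 91.7% and 88.3%.

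Neither test is better for every shape.

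**The case against.** The strongest reply is that 10.8% belongs to a rule the plan does not contain. That is right. A reader might infer that the trial runs at 11% error, but the documents neither state nor exclude an any-contrast rule. The supportable defect is an unstated criterion together with a reason for non-adjustment that does not fit five contrasts.

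A reader might also add the three Week 8 comparisons with placebo and count any of eight tests, which gives 15.9%. That goes further than the text. SAP 6.5.3 places the primary inference in the contrasts, and nothing suggests that one success among eight mixed tests would count. What stands is that the status of these comparisons should be stated. Week 2 adds nothing here, because SAP 6.5.1 already makes it a reference.

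This is also a phase II dose-response study with no declared success threshold. The patterns are prespecified, every contrast p-value will be shown, and estimates come with confidence intervals. Protocol 7.2.4 links the recommended doses to the efficacy and safety profiles together, not to a contrast p-value. All of this limits selective reporting and moderates the consequence. It does not say which result establishes a dose-response.

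Finally, both documents are translations, so the five-coefficient pattern may be a translation or text-reading fault. It calls for a check against the source and is not itself proof of an error in the analysis.

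**Conclusion.** The point holds as a gap in the decision rule and should be fixed. The reason in SAP 6.5.3 does not control error for five contrasts each tested at 5%, and no other text in either document supplies the control. Depending on the rule adopted later, two-sided error could be 0.9%, 5% or about 10.8% (10.1% to 12.5% over readings of the third pattern).

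These figures assume equal groups and complete Week 8 data. Covariates and missing data in the MMRM would shift the correlations somewhat. The conclusion does not depend on how the third pattern is read: the any-contrast rule exceeds 10% under each reading tried.

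**What to change.** In SAP 6.5.3, cross-referenced from 10.1.1.1.1:

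1. State that a Week 8 dose-response is declared if the largest |t| over the prespecified contrasts exceeds the two-sided 5% multivariate-t critical value. Compute that value from the contrasts' estimated correlation matrix in the primary MMRM. Report an adjusted p-value for each contrast.
2. Fix one degrees-of-freedom convention, for example the smallest Kenward-Roger value among the contrasts, because these values can differ by contrast.
3. State that the Week 8 comparisons of each dose with placebo are supportive and descriptive.
4. Check the third pattern against the source and, if it is wrong there, correct it to four coefficients in both documents. Print no numeric critical value until this is done.
5. Restate power at the planned means as about 89% for at least one contrast (about 88% under the other reading), beside 91.7% for (3, 1, -2, -2) alone. These are different claims: (3, 1, -2, -2) itself, at the adjusted critical value, has about 85% (84%).

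The cost is no extra patients, text in two SAP sections, an entry in SAP 2 and one extra computation. Power falls about 2 points from the stated 91.7% (about 4 under the other reading). Bonferroni over five would be dearer, at about 83%.

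An acceptable alternative is to name (3, 1, -2, -2) as the single decisive contrast and make the other four descriptive. That keeps 5% and 91.7%, but gives up power if the response does not plateau between 0.5 and 1.0 μg/kg.

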6.5.4 Multiplicity of multiple analysis sets

For efficacy, the FAS will be used as the primary analysis set, and the PPS will be used for the supplemental analysis to examine the robustness of the results, so multiplicity among multiple analysis sets will not be adjusted. It is not applicable for safety because only the SS is used as the analysis set. It is not applicable for pharmacokinetics because only the PKS is used as the analysis set.

6.6 Use of "Two Different Analysis Sets for Efficacy Evaluation" of Subjects

The primary efficacy analysis set will be the FAS. On the other hand, the analysis will also be performed in the PPS as a supplemental analysis to examine the robustness of the results. The definitions of FAS and PPS are detailed in "4 Analysis Sets."

6.7 Active-controlled Studies Intended to Show Non-inferiority

Not applicable.

6.8 Examination of Subgroups

As the subgroup analyses of efficacy endpoints, the matters shown in "10.3 Efficacy Subgroups" will be performed. As the subgroup analyses of safety endpoints, the matters shown in "12.5 Safety Subgroups" will be performed.

7. Disposition of Subjects

The subjects who entered the treatment period will be analyzed.

7.1 Analysis Sets

The numbers and percentages of subjects will be presented for the analysis sets shown in Table 7.1-1, and between-group imbalance will be examined by Fisher's exact test.

Table 7.1-1 Category

Analysis Sets	Category
FAS	Included, excluded
PPS	Included, excluded
SS	Included, excluded
PKS	Included, excluded

7.2 Presence or Absence and Reasons of Discontinuation

The numbers and percentages of subjects for presence/absence of discontinuation during the treatment period will be presented, and between-group imbalance will be examined by Fisher's exact test.

For the reasons of discontinuation in the treatment period, the number and percentage of subjects will be presented for each category shown in Table 7.2-1.

Statistical Analysis Plan	Protocol No. MR13A9-4
Statistical Alialysis Flair	Version: 1.0

Table 7.2-1 Category

Category	Reason for discontinuation
Adverse event	When the reason for discontinuation during the treatment period entered in the case report form falls under the category of "adverse event"
Lack of efficacy	When the reason for discontinuation during the treatment period entered in the case report form falls under the category of "lack of efficacy"
Withdrawal by subject	When the reason for discontinuation during the treatment period entered in the case report form falls under the category of "Withdrawal by subject "
Protocol deviation	When the reason for discontinuation during the treatment period entered in the case report form falls under the category of "protocol deviation"
Others	When the reason for discontinuation during the treatment period does not fall under the categories of "adverse events," "lack of efficacy," "withdrawal by subject," or "protocol deviation."

8. Demographic and Other Baseline Characteristics

8.1 Subject Demographics

The numbers and percentages of subjects are presented overall and by group for the variables shown in Table 8.1-1 and Table 8.1-2 and summary statistics are presented for the variables shown in Table 8.1-3. However, only the number of subjects is shown for the primary disease of dialysis. If there are data at more than one time point before the start of the treatment period, the data at Week 0 will be used for the evaluation of subject demographic.

The between-group imbalance will be examined by tests for the prior treatment with nalfurafine hydrochloride, specific signs or symptoms to be confirmed in the screening period, dry weight at the start of the screening period (ordinal scale variable), and mean NRS score. Depending on the characteristics of the data, Fisher's exact test will be used for nominal scale variables, Kruskal-Wallis test for ordinal scale variables, and one-way analysis of variance for continuous variables.

Table 8.1-1 Nominal Scale Variables

Item	Category
Sex	Male, female
	Diabetic nephropathy, glomerulonephritis chronic,
Primary disease of dialysis	nephrosclerosis, polycystic kidney, pyelonephritis chronic,
	other, unspecified
Type of dialysis	HD, off-line HDF, on-line HDF, I-HDF
	Arteriovenous fistula, arteriovenous graft, external shunt,
Vascular access	subcutaneously fixed superficial artery, percutaneous venous
	catheter, direct arterial puncture, other
Remaining renal function	No, Yes
Prior treatment with nalfurafine hydrochloride	No, Yes
Specific signs or symptoms to be confirmed in the screening period ^{a)}	No, Yes

a) Specific signs or symptoms: dizziness, syncope, palpitations, tachycardia, fall, seizure, gait disturbance, mental status changes, somnolence, mood changes

Table 8.1-2 Ordinal Scale Variables

Item	Category
Age	$< 65 \text{ years}, \ge 65 \text{ years}$
Dry weight at the start of the screening period	$< 45 \text{ kg}, \ge 45 \text{ and} < 65 \text{ kg}, \ge 65 \text{ and} < 85 \text{ kg}, \ge 85 \text{ kg}$

Statistical Analysis Plan	Protocol No. MR13A9-4
	Version: 1.0

Table 8.1-3 Continuous Variables

Item

Age, dry weight at the start of the screening period, hemodialysis history, single-pool Kt/V, urea reduction ratio, disease duration of itch, mean NRS score, itch score based on the Shiratori's severity criteria (higher of daytime or night-time), Skindex-16 (overall score), 5-D Itch Scale (total score)

